#### 8.3.2 Storage

Treatment packs containing A4250 capsules should be stored and dispensed in accordance with regulations in their original containers. The storage facility at the investigative site should be locked and the storage temperature should be between 15°C and 25°C.

Patients/caregivers should be informed of appropriate storage conditions (i.e., room temperature, between 15°C and 25°C).

Any deviations from the recommended storage conditions should be immediately reported to Albireo and the study drug should not be used until authorization has been given by Albireo.

#### 8.3.3 Blinding and Randomization of Study Drug

A double-blind design is employed so that both the investigators and the patients will be unaware of the treatment assignment during the study.

After written informed consent is obtained from an eligible patient, an 8-digit patient identification number will be assigned. The first 2 digits will denote the country, followed by a 3-digit site number and a 3-digit patient sequence number. This number will be created and

allocated by the Interactive Web Response System (IWRS), when the patient first enters the system at Screening. The randomization codes will be computer-generated by [REDACTED] Biostatistics and kept by a statistician independent from the project team. The randomization will be done in blocks and stratified according to PFIC class (Type 1 and 2) and age class (6 months to 5 years, 6 to 12 years, and 13 to  $\leq 18$  years) to ensure approximate balance between dose schemes (1:1:1). A separate randomization list will be prepared for the maximum 5 patients from Study A4250-003 regardless of stratification. Randomization codes will be assigned sequentially as patients become eligible for randomization.

Patients who are eligible for randomization will be assigned a unique 4-digit randomization number by IWRS. This randomization number identifies which treatment will be allocated to the patient. Patients who withdraw from the study after randomization visit are not to be replaced and their randomization number will not be reused.

To ensure blinding, the study drug and the matching placebo have the same shape and size. Patients will receive capsule(s) of A4250 according to their dose group or capsule(s) of matching placebo once a day during the double-blind Treatment Period. Labels on the study drug containers will not identify the treatment that a patient is randomized to. Traceability of the treatment is ensured by the study drug number.

The 5-digit study drug number will identify study drug packs and will be detailed on the study drug label. Dispensing of study drug will be coordinated by IWRS.

The system will assign a study drug number corresponding to the randomization arm. The randomization number will be used in the background only to ensure no unblinding and will not be displayed to end-users in the IWRS.

#### **8.4 Procedure for Breaking the Randomization Code**

Should a situation arise where unblinding is urgently required, i.e., only where knowledge of the study drug is required to adequately manage a life-threatening situation, the investigator at that study site may perform immediate unblinding through IWRS. The responsibility to break the treatment code in emergency situations resides solely with the investigator. The investigator should make every effort to discuss the rationale (status and outcome) for emergency unblinding with the sponsor Medical Monitor or the [REDACTED] Medical Monitor as soon as possible to review the individual patient details.

The study site investigator and appropriate [REDACTED] project team members will be authorized to access the emergency unblinding functionality within the IWRS. Emergency unblinding takes place in the IWRS via a dedicated emergency unblinding module. The system will require the user to enter their emergency unblinding, which is typically provided at the same time login credentials are distributed. The exact description of the treatment assigned to the individual patient then will be accessible to the user. Once the randomization code is broken for a patient, he/she must be withdrawn from the study and all assessments and procedures at EOT should be performed. As a follow-up, Visit 10, will be performed according to the time

schedule. Once a randomization code has been broken, the investigator must inform the [REDACTED] and sponsor Medical Monitor in writing within 24 hours. In case of technical issues accessing the system online, please see the IWRS site user manual for country-specific contact telephone numbers for the [REDACTED] HelpDesk 24/7 system support.

### **8.5 Patient Compliance**

The study nurse will monitor eDiary compliance by routine review of the CRF health website. If both diary entries on a day are missing, the study nurse will call the patient/caregiver to remind them to complete all scheduled entries. Any noncompliance will be documented and explained in the source documents.

Study drug compliance will also be checked through diary responses. Additionally, patients will return all unused study drug at Visits 4, 5, 6, 7, 8, and 9. The study site staff will count all returned drug, assess compliance, and record details in the eCRF.

Treatment Compliance =  $100 \times ((\text{Number of study drug dispensed} - \text{number of study drug returned}) / \text{number of study drug that should be taken})$ .

Treatment compliance between 80% and 120% will be acceptable.

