### **Screening Period**

Informed consent must be obtained at Visit 1 prior to performing any study procedures. After signing the ICF, patients will be considered enrolled and evaluated for study eligibility.

Daily recording of pruritus using an electronic diary (eDiary) will be started to determine confirmation of the magnitude and the baseline pruritus symptoms before the study. After consultation with the Medical Monitor, patients failing eligibility criteria may be re-screened. Patients not fulfilling inclusion/exclusion criteria after 3 attempts are not allowed to re-screen.

Caregivers/patients will be instructed on the daily use of the eDiary. The eDiary will include patient-reported outcome (PRO) and observer-reported outcome (ObsRO) items for evaluation of itching (PRO), scratching (ObsRO), and sleep disturbance (PRO and ObsRO) during the Screening Period (study Days -56 to 0), throughout the 24-week Treatment Period (study Days 0 to 168), and Follow-up (Day 196).

The 14 consecutive days prior to randomization will be used for eligibility calculation of the diary entries. If a patient does not meet the minimum number of observations (see [Section 9.2.2](#) for scoring and missing data definitions) to determine eligibility, the patient may be re-screened. Observer-reported outcomes in patients of all ages will be recorded by a caregiver. If possible, the same caregiver will complete the Albireo ObsRO items throughout the study.

At a second Screening Visit (Visit 2) additional laboratory samples will be taken for eligibility assessments.

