### 7.2.1 Inclusion Criteria

1. A male or female patient, with clinical diagnosis of PFIC Type 1 or 2, between the ages of  $\geq 6$  months and  $\leq 18$  years at Visit 1 with a body weight above 5 kg
2. Patient must have clinical genetic confirmation of PFIC-1 or PFIC-2 through identification of biallelic pathogenic variants in either the *ATP8B1* or *ABCB11* genes
3. Patient must have elevated s-BA concentration, specifically measured to be  $\geq 100$   $\mu\text{mol/L}$ , taken as the average of 2 samples at least 7 days apart (Visits 1 and 2) prior to randomization
4. Patient must have history of significant pruritus and a caregiver-reported observed scratching in the eDiary average of  $\geq 2$  (on 0 to 4 scale) in the 2 weeks prior to randomization
5. Patient and/or legal guardian must sign informed consent (and assent) as appropriate. Patients who turn 18 years of age (or legal age per country) during the study will be required to re-consent in order to remain in the study
6. Patients will be expected to have a consistent caregiver for the duration of the study
7. Caregivers and age-appropriate patients ( $\geq 8$  years of age) must be willing and able to use an eDiary device as required by the study

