## 9 ASSESSMENT OF EFFICACY

### 9.1 Efficacy Endpoints

#### 9.1.1 Primary Efficacy Endpoint

The primary efficacy endpoints are as follows:

- **European Union (EU) and rest of the world (RoW):** Proportion of patients experiencing at least a 70% reduction in fasting s-BA concentration from baseline to the end of treatment or reaching a level  $\leq 70$   $\mu\text{mol/L}$  compared to placebo after 24 weeks of treatment.

Fasting s-BA baseline will be calculated as the average of the value at randomization and the previous visit (Clinic Visit 2). The end value is the average of the values at Weeks 22 and 24 after the start of double-blind treatment.

- **United States (US):** Proportion of positive pruritus assessments at the subject level over the 24-week Treatment Period. A positive pruritus assessment is defined as a scratching score of  $\leq 1$  or at least a one-point drop from baseline on the Albireo ObsRO instrument. At each assessment, the AM score will be compared to the AM baseline, and the PM score will be compared to the PM baseline. Both AM baseline and PM baseline pruritus assessments will be included in the analysis of this endpoint. AM scores from the 14 days prior to the first dose of study medications will be averaged as AM baseline. PM scores from the 14 days prior to the first dose will be averaged as PM baseline.

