### **9.2.2 Itching, Scratching and Sleep Score**

Itching, observed scratching, and sleep disturbance will be recorded twice each day via eDiary. Patients and/or caregivers will be instructed to complete the eDiary every day in the morning after the patient wakes and in the evening just before the patient goes to sleep throughout the study. Patients and caregivers will receive a formal training session during Visit 1.

The eDiary includes Albireo ObsRO and PRO items. Patients <8 years of age will not be asked to complete the Albireo PRO items; only the Albireo ObsRO will be completed by caregivers of patients in this age group. Older patients, 8 to 18 years of age, will complete the Albireo PRO items and the caregiver will complete the Albireo ObsRO items. The Albireo PRO items assess severity of itch, aspects of sleep disturbance (morning diary only), and tiredness. For patients 8 to 12 years of age, the caregiver will read the Albireo PRO items along with the child and record the child's response. A guide will be provided to the caregivers that provides standardized explanations of the Albireo PRO items, in case the patient is confused or requires clarification about the meaning of a question. The Albireo ObsRO items assess severity of observed scratching, aspects of observed sleep disturbance (morning diary only), and observed signs of tiredness (evening diary only). The Albireo ObsRO and PRO scratching and itch severity items use 0 to 4 response scales, where each response is distinguished by a unique facial expression, verbal anchor, number, and color code ([Appendix 2](#)). To meet eligibility criteria, a scratch score will be calculated from daily diary entries (ObsRO items) the 14 consecutive days prior to randomization.

A daily AM & PM score for the Albireo ObsRO scratching item will be averaged from the 2 ratings for each day. A daily score will be considered missing if both of the daily assessments are missing. A weekly score will be calculated by averaging the daily scratching scores. A weekly score will be considered missing if  $\geq 4$  out of 7 days a week of data are missing. For AM & PM baseline, a 14-day daily score of AM & PM prior to the first dose of study medications will be averaged as the baseline score.

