#### **11.2.2.2 Missing Data**

In the primary analysis of the pruritus endpoint, all intermittently missing assessments will be classified as negative pruritus assessments. Similarly, all planned assessments after the intercurrent events (premature treatment discontinuation, death or initiation of rescue treatments such as biliary diversion surgery or liver transplantation) will be counted as negative pruritus assessments. However, as described above, all 336 assessments planned over the 24-week treatment period will be included in the denominator of the endpoint definition.

In the primary analysis of fasting bile acid responder endpoint, dropouts and patients with a missing average at the end of the treatment will be treated as non-responders. Patients in need of surgical rescue, i.e. biliary diversion and listing for liver transplant will be classified as non-responders. Continued collection of efficacy data for patients who discontinue treatment will be made as far as possible.

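### Diary completeness is checked by day, but the US primary pruritus endpoint is scored by half-day, so once-a-day logging triggers no reminder call and caps a child's score at 0.50

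*Protocol*

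**What the plan says.** Rules set by day:

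- Section 8.5, reminder call: "If both diary entries on a day are missing, the study nurse will call the patient/caregiver to remind them to complete all scheduled entries".
- Section 9.2.2, daily score: "A daily score will be considered missing if both of the daily assessments are missing". One entry is enough.
- Section 9.2.2, weekly score: "A weekly score will be considered missing if" four or more of the seven days are missing. The unit is again the day.
- Section 7.1.1 (Screening Period), eligibility: "If a patient does not meet the minimum number of observations", re-screening is possible. The minimum itself is left to section 9.2.2.
- Section 7.2.1, criterion 4: "a caregiver-reported observed scratching in the eDiary average of" at least 2 over the two weeks before randomization, with no separate AM or PM requirement.

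Rules set by half-day:

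- Section 9.2.2, collection: "Itching, observed scratching, and sleep disturbance will be recorded twice each day via eDiary".
- Section 9.1.1, US primary endpoint: "the AM score will be compared to the AM baseline, and the PM score will be compared to the PM baseline". Each baseline is the mean of its own scores over the 14 days before first dose.
- Section 11.2.2.1, ANCOVA: the AM baseline and the PM baseline enter as two covariates.
- Section 11.2.2.2, missing data: "all intermittently missing assessments will be classified as negative pruritus assessments", and all 336 planned assessments remain in the denominator.

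**The concern.** The day-based rules suit a daily average score, which one entry can supply. They do not suit an endpoint in which each morning and each evening is a separate success or failure. A family that reliably fills in the diary once a day meets the only condition that would prevent a call, yet half of the child's assessments are scored as treatment failure whatever the itch was.

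Three things are at stake. Logging habit enters the primary endpoint as lack of effect. Where habits differ between children, they add variance unrelated to treatment, with about 20 children per arm. And a child may be randomized without one of the two baselines that the endpoint definition and the model both need. Missed mornings also remove the sleep-disturbance items, which section 9.2.2 places in the morning diary only.

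**Working it through.** **Step 1. The plan's denominator.** Two entries a day (9.2.2) over 24 weeks (11.2.2.2): 24 × 7 × 2 = 336. This agrees with the protocol.

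**Step 2. One entry a day throughout treatment.**

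- Recorded: 24 × 7 = 168. Missing, hence negative: 336 − 168 = 168, or 168/336 = 50%.
- Highest attainable proportion: 168/336 = 0.50.
- Days with both entries missing: 0, so calls triggered under 8.5: 0.
- A shorter lapse also counts. Visits 6 and 7 are on Days 84 and 126, 42 days apart. Missing every morning between them costs 42/336 = 12.5% of the denominator, again with no call.

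**Step 3. Entry with 14 PM and no AM entries.**

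- Valid daily scores: 14 of 14. Both weekly scores are valid, and the average can reach 2.
- AM baseline: a mean of 0 values, so undefined.
- An AM entry of 1 or less is still positive. The one-point-drop route cannot be assessed for AM entries, and one stated ANCOVA covariate is missing.

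**Step 4. The plan's power figure.** Inputs from section 11.1: effect size 1.0526, 20 per arm, 1-sided 0.025. A single two-sample t comparison has noncentrality 1.0526 × √(20/2) = 3.33 on 38 df and power 90.0%. Simulating the closed test (pooled doses first, then each dose; two-sample t; 40,000 runs) gives:

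| Claim | Simulated | Protocol |
|---|---|---|
| Particular arm | 89.6% | 89% |
| At least one arm | 95.7% | 95% |
| Both arms | 83.2% | 83% |

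The stated figures reproduce.

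**Step 5. What once-a-day logging could do to power.** The protocol gives no mean, SD or rate of missed entries, so these are assumptions:

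- effect size 1.0526 taken as 0.20/0.19, 0.30/0.285 or 0.40/0.38;
- placebo mean 0.2 for all three, and also 0.3 for the first;
- once-a-day children occur at random at the same rate in every arm, with their proportion halved;
- normal outcomes, variance pooled over three arms, no covariates, 20,000 runs.

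| Share logging once daily | Particular-arm power | With outcomes clipped to 0-1 |
|---|---|---|
| 0% | about 90% | 88-90% |
| 10% | 85-88% | 85-86% |
| 20% | 80-86% | 80-83% |
| 50% | 68-81% | 68-76% |
| 100% | about 90% | 88-90% |

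The last row shows the mechanism. If every child misses the same share m, the difference D and the standard deviation SD both shrink by (1 − m), and (1 − m)D / ((1 − m)SD) = D/SD. The estimated difference is smaller but power does not change. Power is lost only when logging differs between children.

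**The case against.** The strongest reply is that the call is not the only control. Section 8.5 also provides for routine review of the diary website and for any noncompliance to be documented and explained. Section 7.1.3 has the diary reviewed for compliance at Visit 2, at Visit 3 (where entry requirements are also checked), at the Day 14 call and at every later visit. Inclusion criterion 7 requires caregivers willing and able to use the device as the study requires, and section 7.2.3 lists substantial eDiary noncompliance among the reasons for withdrawal. A reader might infer from the call rule that a half-empty diary would go unnoticed for 24 weeks. The documents do not support that. What stands is that none of these controls sets an AM or PM threshold or requires contact for a missed half-day. Withdrawal would not recover the data either, since assessments planned after premature treatment discontinuation also count as negative.

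A second reply is that a missing AM baseline is a matter for the SAP. That is fair. A reader might infer that such a child must fall out of the ANCOVA, but the SAP is not shown and may have a rule. It cannot restore entries that were never made.

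Third, applying the weekly rule twice suggests that 2 × 4 days × 1 entry = 8 of 28 entries suffice for eligibility. This is only an inference: section 9.2.2 uses the rule to define a weekly score and never says that two valid weekly scores are the 14-day minimum. Step 3 does not rely on it.

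Finally, a reader might infer bias between arms. That would need logging to differ by arm; nothing in the protocol indicates that it does, and the trial is double-blind.

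**Conclusion.** The mismatch is real and follows from the protocol's own wording: reminders and completeness rules run by day, the US primary endpoint by half-day. Two consequences are certain as arithmetic. Once-a-day logging triggers no call and caps the score at 0.50, and no stated rule prevents 14 valid baseline days from containing no AM entry.

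How often either would happen is unknown. The fall in particular-arm power from about 90% to 85-88%, if 10% of children log once daily, is an illustration under assumed means and SDs. It comes from variation between children. It would be wrong to read the smaller absolute difference under uniform missingness as a loss of power.

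This does not invalidate the endpoint or its analysis. It is a cheap improvement that protects data which no later analysis can recover.

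**What to change.** - **Section 8.5:** trigger the reminder (device alert, nurse call, or both) on missed AM or PM ObsRO entries, rather than only when both are missing on one day; for example, after two consecutive missed AM entries or two consecutive missed PM entries.
- **Sections 7.1.1 and 9.2.2:** state the eligibility minimum for the 14 baseline days explicitly, as a number of AM entries and, separately, a number of PM entries. One option is the threshold already implied by the weekly rule (7 − 3 = 4 of 7 days present), applied to each half-day in each week. If it is not met, re-screen, as section 7.1.1 already permits. Simply lengthening screening is not clearly allowed within the 35- to 56-day period.

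The numbers in both examples are suggestions; the essential change is that the unit matches the endpoint. The cost is protocol wording, possibly an alert setting, more reminder contacts by existing staff and a few re-screenings. No assessment is added, and the endpoint and its analysis stay as they are.

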### **8.6 Study Drug Accountability**

Records shall be maintained of the delivery of study treatment(s) to the study site(s), of the inventory at the study site(s), of each use of the study treatment(s) for each patient, and of the return of unused study treatment(s) to Albireo.

These records shall include dates, quantities, batch numbers, expiry dates, and the unique code numbers assigned to the study drug and to the study patients.

The investigator will be responsible for ensuring that the records adequately document that the patients were provided the quantities specified in the protocol and that all study drug received from Albireo is reconciled.

### **8.7 Concomitant Therapy and Prohibited Medications**

The investigator will note all ongoing medication and any medication recently stopped (within 1 month prior to Visit 1) in the eCRF. At Visits 2 through 10, all changes in medication (stopping or starting new medication or changes in dose) will be recorded in the eCRF. All medications (prescribed or over the counter) for pruritus and sleep will be recorded.

All medications taken by a patient within 3 months prior to the first intake of study drug are regarded as prior medication.

All medications taken by a patient on or after the first intake of study drug, and which continue to be taken during the study, are regarded as concomitant medication.

Prohibited medications are listed in [Appendix 1](#).

## 9 ASSESSMENT OF EFFICACY

### 9.1 Efficacy Endpoints

#### 9.1.1 Primary Efficacy Endpoint

The primary efficacy endpoints are as follows:

- **European Union (EU) and rest of the world (RoW):** Proportion of patients experiencing at least a 70% reduction in fasting s-BA concentration from baseline to the end of treatment or reaching a level  $\leq 70$   $\mu\text{mol/L}$  compared to placebo after 24 weeks of treatment.

Fasting s-BA baseline will be calculated as the average of the value at randomization and the previous visit (Clinic Visit 2). The end value is the average of the values at Weeks 22 and 24 after the start of double-blind treatment.

- **United States (US):** Proportion of positive pruritus assessments at the subject level over the 24-week Treatment Period. A positive pruritus assessment is defined as a scratching score of  $\leq 1$  or at least a one-point drop from baseline on the Albireo ObsRO instrument. At each assessment, the AM score will be compared to the AM baseline, and the PM score will be compared to the PM baseline. Both AM baseline and PM baseline pruritus assessments will be included in the analysis of this endpoint. AM scores from the 14 days prior to the first dose of study medications will be averaged as AM baseline. PM scores from the 14 days prior to the first dose will be averaged as PM baseline.

